- Compare monthly RDT consumption data and volumes/TPRs reported via the registers and HMIS/DHIS2 with manual counts of used RDTs and RDT positives collected from health facilities and CHWs in monthly counts. A digital tool will be used alongside the manual counting process to take pictures of each RDT counted and provide the RDT test result.
- Identify discrepancies between reported and manual RDT counts, TPRs and ACT consumption and discuss these in monthly validation meetings.
- Observe whether discrepancies will disappear over time:

⁸ Cameroon National Malaria Control Program annual report, 2022.

⁹ Cameroon DHIS2, 2022

- Manually and digitally counted RDT volumes and positives converge with what is reported in registers/DHIS2
- Manually and digitally country RDTs and RDT positives will converge with reported RDT and ACT consumption volumes
- Assess operational feasibility, costs, and acceptability of the manual RDT storage and count method.

Participating health care workers and CHWs in study sites will be informed about the manual count and asked to store all used RDTs in labeled storage containers that will be provided for this purpose. HCW/CHW are expected to conduct business as usual, interpreting and reporting RDTs per national guidelines and recording the RDT results. At the end of each month, supervisors will collect and count the RDTs. The number of positive and total RDTs will be manually recorded and totals will be compared with the register and DHIS2 reported RDT country and positives.

Primary outcome:

• The primary outcome will be a comparison of the volume and test positivity rate (TPR) from the manual counts by trained supervisors to the TPR recorded in the HMIS (historic, surrounding areas, by CHWs and HF) on a monthly basis over the course of the 6-month intervention.

Secondary:

The secondary outcomes of this study are to:

- 1. Compare the manually counted RDTs and RDT positives to what was recorded in the registers
- 2. Compare the manually counted RDTs and RDT positives to the consumption of RDTs and ACTs recorded in the DHIS2 and pharmacy records (i.e., supply log)
- 3. Compare the costs of implementing the monthly RDT validation with potential savings from reductions in prescription of ACTs
- 4. Measure the impact of monthly RDT validation exercises on changes in HCWs' subjective norms, attitudes, perceptions and practices related to RDTs

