nurses in charge of the participating health facilities after each count. The supervisors and the district health official will participate in the monthly count process, facilitated and chaired by the research team (at least for the first few months). Participants in the counting process will receive brief training on manual RDT result interpretation by the research team and use of the digital tool (a mobile app downloaded on a phone).

Sampling calculation

We hypothesize that the TPR recorded in the registers differs from the TPR found through the manual count and used the anticipated difference in our sample size calculations. We calculated sample size requirements based on a cluster randomized two-sample unpaired t-test for the comparison of two proportions using standard formulae (Hayes and Bennett, 1999). We fixed the Type 1 error at 5% and the power at 80%. Prior to the intervention we assume the TPR to be 65% in HFs and 95% in CHWs. We hypothesize that this, as a result of our intervention, will decrease to 40% in HFs and 50% in CHWs. We accordingly calculated separate sample sizes for HFs and CHWs based on the baseline and expected proportions. Since we will be sampling HFs and CHWs, we expect that there will be clustering effects in the populations that these Point Of Care serve. As such, we took clustering into account by applying a design effect based on the total population (i.e. total number of tests) that these POCs cover over six months (the assumed sampling time period) - using 2023 testing data for all HFs and CHWs in East region. We used an ICC of 0.05. Based on these assumptions and calculations, the maximum sample size required for HFs and CHWs respectively is 2121 and 1292 tests. We aim to sample from 16 HFs and 31 CHWs over a single district in the East region to control unknown confounders and differences in behavior/population between HFs and CHW catchment populations.

Tools for data collection

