2	Secondary	The proportion of RDTs reported as positive in months prior to intervention and in surrounding HF and CHWs	TPR calculated during the monthly validation meetings will be compared to the TPR found in the DHIS2 of HF in surrounding districts and in the TPR of intervention HF and CHWs attached to that HF in the same month in the three previous years.
		The total number of positive RDT found in the manual count and the total volume of ACTs administered	The total count of positive RDTs during the monthly validation meeting for each HF and CHWS attached to the HF will be compared to the total count of ACTs administered at that HF and by CHW attached to that HF during the same period, as recorded in the institution's supply log.

Total costs associated with monthly RDT counts	Collection and analysis of cost data, including personnel costs, travel expenses, and other project-related expenses will be used to estimate the total costs associated with the RDT counts
HCWs subjective norms, attitudes, perceptions and practices regarding RDT usage	A survey will be administered to participating HCWs to understand their subjective norms, attitudes, perceptions and practices regarding RDT
Acceptability and feasibility of implementing monthly RDT validation exercises	In-depth interviews will be conducted with HCWs, health officials to understand their perceptions of the acceptability of the monthly validation processes

Potential Risks

We do not foresee direct risks to participants in the study. One potential risk would be in health outcomes if fewer ACTs are administered. In Benin, where the manual count has already been rolled out, no significant impacts were recorded related to increases in morbidity and mortality in the intervention areas. The proposed intervention would not deviate from existing national guidelines in which ACTs should only be administered to patients with a parasite-based positive diagnosis (i.e., microscopy or RDT).

Loss or damage of RDT cassettes before validation is a potential risk to the study fidelity. As a mitigation, an SOP for proper storage of RDT cassettes will be provided to participating health workers for the safe handling and retention. Regular checks, especially in the first few months will also be conducted to ensure adherence to storage protocols.

Participant Enrollment and informed consent

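### The historical and surrounding-district comparison sets cassette-counted positivity against DHIS2-reported positivity, so it cannot show whether reporting changed

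*Protocol*

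**What the plan says.** The Study Outcome Measures table has a secondary row named "The proportion of RDTs reported as positive in months prior to intervention and in surrounding HF and CHWs". Its method column says "TPR calculated during the monthly validation meetings will be compared to the TPR found in the DHIS2 of HF in surrounding districts", and adds a comparison with the "TPR of intervention HF and CHWs attached to that HF in the same month in the three previous years".

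The primary outcome under AIM and Outcomes contains the same contrast. It sets volume and TPR "from the manual counts by trained supervisors to the TPR recorded in the HMIS (historic, surrounding areas, by CHWs and HF".

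The Sampling calculation section states two hypotheses. The first concerns measurement: "We hypothesize that the TPR recorded in the registers differs from the TPR found through the manual count". The second concerns change: "Prior to the intervention we assume the TPR to be 65% in HFs and 95% in CHWs", followed by "We hypothesize that this, as a result of our intervention, will decrease to 40% in HFs and 50% in CHWs".

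Under Data analysis, the protocol also plans a mixed model with separate pre/post and reported/counted indicators. It further plans a plot of the ratio of register TPR to cassette TPR, to be set beside the change in DHIS2 TPR.

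**The concern.** Used cassettes are stored and counted only in the study district and only during the six study months. The figures for surrounding districts and for earlier years can therefore only be reported TPR. When the comparison moves from the study district to another district, or from the study months to an earlier year, the measuring method changes with it.

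This would matter little if the two methods were expected to agree. The protocol expects the opposite and builds its sample size on the gap. Its literature review also cites a study in the Democratic Republic of Congo with 22% by automated reader against 69% in the HMIS, a difference of 47 points.

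The aim is that counting and feedback bring reported figures towards the count. Success therefore shows as movement in reported TPR in the study district, and that quantity does not appear in this contrast. The row is also the only specified comparison that has an external control or matches calendar months, so the part of the plan best placed to deal with season and secular trend does not address the question.

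**Working it through.** **1. The two sides of each comparison**

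| Comparison | Study side | Comparator |
|---|---|---|
| Surrounding districts, same period | Cassette count | DHIS2-reported TPR |
| Study sites, same months of three earlier years | Cassette count | Reported TPR (the primary outcome names the HMIS; no cassettes were kept then) |
| Study sites, same month (primary row of the table) | Cassette count | Register and DHIS2 TPR |

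In the first two rows, method changes together with district or period. In the third, only method changes, so that row is a clean measure of discordance.

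**2. Inputs**

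The Sampling calculation gives 65% (HF) and 95% (CHW) before the intervention, and 40% and 50% as the anticipated lower values. The same pairs serve there both as the register-versus-count difference and as the expected decrease. The plan's own differences are 40 - 65 = -25 points and 50 - 95 = -45 points.

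The stated sample sizes (2121 and 1292 tests) cannot be reproduced, because the number of tests per point of care behind the design effect is not given. Nothing below depends on them.

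*Assumption for illustration:* the cassettes read 40% and 50% throughout, and DHIS2 TPR in earlier years and in surrounding districts is 65% and 95%.

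**3. Formulae**

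Let R0 be reported TPR earlier or elsewhere, C the counted TPR during the study, and f the share of the reporting gap that closes in the study district.

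- Reported TPR in the study district during the study: R1 = R0 - f(R0 - C)
- Planned contrast: C - R0 (f does not appear)
- Like-for-like contrast: R1 - R0 = -f(R0 - C)
- Part of the planned contrast due to method alone: C - R1 = -(1 - f)(R0 - C)

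The planned contrast is the sum of the last two: C - R0 = (R1 - R0) + (C - R1).

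**4. Results, in percentage points**

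| Share of gap closed | Planned, HF | Like for like, HF | Method alone, HF | Planned, CHW | Like for like, CHW | Method alone, CHW |
|---|---|---|---|---|---|---|
| 0% | -25 | 0 | -25 | -45 | 0 | -45 |
| 50% | -25 | -12.5 | -12.5 | -45 | -22.5 | -22.5 |
| 100% | -25 | -25 | 0 | -45 | -45 | 0 |

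With C held fixed, the planned contrast is the same in every row, whatever happens to reporting. The structure holds for any gap; only its size scales.

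**5. Do the other planned analyses supply the missing piece?**

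- *Mixed model.* Counted TPR exists only after introduction. If reported TPR is entered for both periods, the pre/post term can pick up R1 - R0 and the reported/counted term C - R1. That partly separates method from period within the study sites. The model has no term for surrounding districts, and its month variable counts time since the counts began, not calendar month.
- *Ratio plot.* It sets reporting against cassettes month by month beside the DHIS2 change. It is descriptive and confined to the study sites.

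Neither provides the external, calendar-matched contrast in reported TPR.

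**The case against.** The strongest reply is that the row does not claim an effect. It says only that figures will be compared, in a study described as an observational pilot whose first aim is the degree of discordance. Counted TPR beside DHIS2 TPR elsewhere can be read as context for how plausible the reported rates are. This is fair. A reader might infer that the protocol will report the difference as the effect of the intervention, but the row names no effect and no test. The causal wording stands in the Sampling calculation.

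A second reply is that whether reporting improved is addressed elsewhere: in the mixed model, in the ratio plot and in the monthly same-site comparison. This also stands in part. If nothing changed in reporting, the same-site comparison would show an unchanged gap every month, and a careful reader of the whole plan would not be misled. It is tempting to say that the remaining pre/post analyses are simply confounded by season. The documents do not support that: the baseline months are not defined, and a statistical analysis plan could match them to the calendar.

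Third, 25 and 45 points might be taken as the expected bias. They are not. They are the upper end of an assumed scenario that takes the protocol's hypothesised values as cassette readings.

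None of these replies makes the row itself informative about reporting, and none supplies a like-for-like comparison with surrounding districts.

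**Conclusion.** The point stands for this comparison, as something that should be fixed. In the historical and surrounding-district contrast, measuring method is fully confounded with period and with district, so the contrast cannot show whether reporting changed.

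On the assumed values, the part due to method alone lies anywhere from 0 to 25 points for HFs and from 0 to 45 points for CHWs, depending on how far reporting converges. This rests on three assumptions: cassettes at 40% and 50%, earlier and external DHIS2 TPR at 65% and 95%, and no shift in the cassette TPR itself. The true gap is unknown.

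The same-site, same-month discordance comparison is sound and is not affected. The outcome table classes the mixed contrast as secondary, and data collection in the study district need not change. The primary outcome wording does, however, include it, so both places need the correction.

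**What to change.** - **Historical and surrounding-district comparison:** use DHIS2-reported TPR on both sides, matched by calendar month. One form is a difference-in-differences: the change in reported TPR in the study district from the same months of the three earlier years, minus the corresponding change in surrounding districts.
- **Counted versus reported TPR:** keep this only as a discordance measure within the same point of care and month. If the existing mixed contrast is also kept, label it descriptive.
- **Surrounding CHWs:** extract their DHIS2 data. The outcome name includes them, but the method lists only HFs for surrounding districts.
- **Primary outcome under AIM and Outcomes:** reword it so that the historic and surrounding-area part follows the same rule and agrees with the outcome table on whether it is primary or secondary.

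**Cost:** changes of wording, a little more analysis, and a small added DHIS2 extraction for surrounding CHWs. With one intervention district, causal conclusions stay limited even after the change, and the report should say so.

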Malaria remains a leading public health challenge in Cameroon, with diagnostic accuracy and data quality among the key barriers to effective case management⁴. The country relies heavily on rapid diagnostic tests (RDTs), with 69% of patients tested using RDTs in 2023⁵. However, very high Test Positivity Rates (TPRs) and supply chain inefficiencies raise concerns about the accuracy of reported malaria cases in Cameroon⁶: Providers may not interpret the test accurately or may report negative RDTs as positive. This could lead to inflated case counts and incidence which distort trends and contribute to observed lack of progress in reducing malaria burden. In addition, administering these patients antimalarials may not address the true cause of illness which can increase the risk to patients for morbidity and mortality. Finally, irrational ACT use may contribute to stockouts as well as wastage and increased risk of developing antimalaria resistance.

Data from the District Health Information System (DHIS2) show that TPR varies widely across Cameroon, with the Southwest reporting rates as high as 89% among public sector health workers, while some regions reporting in the lower 60% range. The Annual Blood Examination Rate (ABER) is highest in the East, Adamawa and Far North regions, ranging between 15-26% (including active testing). The average TPR among Community Health Workers (CHWs) is 83%, significantly higher than in health facilities, with minimal variation between age groups. While it is plausible that CHWs, as first-line responders, test only febrile patients with a high likelihood of malaria, qualitative data suggest that other factors may be influencing these high positivity rates. Key Informant Interviews (KIIs) with malaria experts in Cameroon conducted by CHAI in 2023 for example indicate that financial incentives tied to reporting positive cases could be a factor, leading to potential overreporting of malaria cases⁷.

The high TPR has led to questions around the accuracy of reporting the test results by health worker (HW) and community health workers (CHW). Previous efforts in other low- and middle-income countries have shown discrepancies between reported and 'true' TPRs (i.e., using

¹ WHO Malaria Guidelines 2023

² A review of the WHO malaria rapid diagnostic test product testing program (2008–2018): performance, procurement and policy. Jane Cunningham, 2019.

³ World Malaria Report, WHO, 2024.

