All health workers (n=32 - 2 per HF) and CHWs (n=31) in the Garoua Boulai health district will be approached for consent and included in the study. We anticipate collecting a minimum of 2121 tests conducted during the study period in outpatients and 1292 tests conducted in the community by polyvalent CHWs.

Inclusion/Exclusion Criteria

PARTICIPANTS- health workers in participating health facilities and CHWs in health areas (catchment) tasked to conduct the malaria RDT in patients suspected of having malaria

INCLUSION CRITERIA:

- All RDTs conducted in outpatients suspected of having malaria by participating CHWs in the targeted health area
- All RDTs conducted by participating healthcare workers on patients at the HFs
- All healthcare workers and community health workers that provided consent to participate in the study

EXCLUSION CRITERIA:

- RDTs conducted by CHWs on pregnant women (Because tests from pregnant women carried out by CHWs are not recorded in the DHIS2) or in patients
- Nonconsenting HCWs

Study Design

This is an observational pilot conducted over six months in the Garoua-Boulaï Health District. It will involve 16 health facilities and 31 CHWs routinely performing malaria testing. The selected district was selected because (i) historic testing data would suggest we could easily meet the sample size of 2121 tests in a period of 6 months in the HFs, (ii) the research team already has ongoing operations in the district, (iii) CHWs carry out Integrated Community case management (ICCM). In collaboration with district health officials and the nurse in charge of the participating health facilities, the health workers, supervisors and the community health workers in the district that conduct malaria RDTs will be invited to a short training in which the study will be explained. The health workers will be informed of the manual count of the RDTs and equipped with containers for storage of the used RDTs. They will be requested to store the used RDT readers be it positive or negative. Supervisors will collect the stored readers monthly for the manual and digital review and counting. Discrepancies will be communicated back to

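### Counted TPR rests only on the cassettes that audited workers hand in, so selective loss of negatives would shrink the measured discordance, and the planned analyses have no place for it

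*Protocol*

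**What the plan says.** **Who holds the evidence.** Under AIM and Outcomes, participating workers are told of the count and "asked to store all used RDTs in labeled storage containers that will be provided for this purpose". Then: "At the end of each month, supervisors will collect and count the RDTs". Study Design words storage as a request: "They will be requested to store the used RDT readers be it positive or negative". The digital count photographs the same returned cassettes.

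**Why retention might be selective.** The background raises the possibility that providers report negative tests as positive. For CHWs it relays expert opinion that "financial incentives tied to reporting positive cases could be a factor".

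**How loss is handled.** Potential Risks says: "Loss or damage of RDT cassettes before validation is a potential risk to the study fidelity". The response is a storage SOP and regular checks, with emphasis on the early months. The section on enrollment and consent adds monthly visits throughout, which verify storage and collect or copy the registers. Selective non-return is not mentioned.

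**What is analysed.** The quantitative part of Data analysis specifies a chi-squared test of reported against counted TPR, a mixed model with TPR as the outcome, and a plot of register TPR over cassette TPR across six months. The plot, set against the DHIS2 trend, is meant to separate provider behaviour from changes in the DHIS2 data.

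**What else is compared.** Volume is named in the primary outcome. The primary row of the outcome table compares counts and positives each month with registers and DHIS2. The second secondary outcome adds RDT and ACT consumption, although the supply-log row of the table names only ACTs: "The total number of positive RDT found in the manual count and the total volume of ACTs administered".

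**The concern.** A worker who records a negative test as positive has a reason not to store the cassette that contradicts the entry. Counted TPR is positives divided by cassettes received, so each missing negative raises it towards the reported figure. The register-to-cassette ratio then falls towards 1 while every register and DHIS2 entry stays the same.

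The protocol offers two explanations for movement in that ratio, provider behaviour and DHIS2 changes. Changed cassette retention is a third, and it has no place in the plan. It could also follow time: discrepancies are fed back after each count, so workers can learn, and some of the scrutiny is concentrated in the early months. A retention trend of that kind would resemble the shrinking discrepancy that the study hopes to see.

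At stake are the size of the discordance, its trend over six months, and the explanation given for that trend.

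**Working it through.** The protocol gives no cassette-recovery rate, so there is no stated figure to reproduce. The calculation below is an illustration.

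**Inputs**
- Reported TPR, R: 65% (HF) and 95% (CHW), from Sampling calculation: "Prior to the intervention we assume the TPR to be 65% in HFs and 95% in CHWs". Held unchanged.
- True cassette TPR, T: 40% (HF) and 50% (CHW). The protocol gives these as the values expected after the intervention. Using them as the true cassette TPR is an assumption.
- Loss, L: share of all cassettes not returned, all of them negative. The values are assumed.
- If over-reporting consists only of negatives recorded as positive, such cassettes make up R − T of all tests: 25% (HF) and 45% (CHW). These are the extremes for this mechanism.

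**Effect on the TPR contrast**

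Counted TPR = T / (1 − L); gap = R − counted TPR; ratio = R / counted TPR.

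| Setting | L | Counted TPR | Gap (points) | Ratio |
|---|---|---|---|---|
| HF | 0 | 40.0% | 25.0 | 1.63 |
| HF | 15% | 0.40/0.85 = 47.1% | 17.9 | 1.38 |
| HF | 25% (extreme) | 0.40/0.75 = 53.3% | 11.7 | 1.22 |
| CHW | 0 | 50.0% | 45.0 | 1.90 |
| CHW | 45% (extreme) | 0.50/0.55 = 90.9% | 4.1 | 1.045 |

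Even when every misreported negative is withheld, a gap remains.

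**What full TPR convergence would need**

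The fraction d of all negatives withheld that makes counted TPR equal R is d = 1 − T(1 − R) / [R(1 − T)].
- HF: 1 − (0.40 × 0.35)/(0.65 × 0.60) = 64.1% of negatives, or 0.60 × 0.641 = 38.5% of all cassettes.
- CHW: 1 − (0.50 × 0.05)/(0.95 × 0.50) = 94.7% of negatives, or 0.50 × 0.947 = 47.4% of all cassettes.

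Counted volume would then be only 61.5% (HF) or 52.6% (CHW) of registered volume. Counted positives would be the same shares of reported positives: 40/65 and 50/95.

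**What the recorded totals can recover**

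Per 100 registered HF tests with 15 negatives missing, there are 40 counted positives and 85 cassettes.
- Recovery ratio: 85/100 = 85%.
- Bounds on counted TPR: 40/100 = 40% to (40 + 15)/100 = 55%. The gap is therefore 10 to 25 points.
- Excess positives: (65 − 40)/100 = 25 per 100, unchanged by the loss.

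Random loss behaves differently. With perfect reporting at 40% and 15% random loss, counted positives are 0.85 × 40 = 34. Counted TPR is 34/85 = 40%, which is correct. The lower bound is 34% and excess positives show a false 6 per 100. The upper bound is (34 + 15)/100 = 49%, so the interval still contains the reported 40%.

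**The case against.** The strongest reply is that the plan already looks at more than TPR. Volume belongs to the primary outcome, convergence under AIM and Outcomes is defined on volumes and positives, RDT consumption is compared, and storage is verified monthly. Withholding negatives leaves the gap in positives unchanged and opens a gap in volume. This stands: a large shortfall would be seen, and by the protocol's own definition it would not be convergence. Visibility is not correction, however. The test, the model and the ratio all use TPR alone, and a moderate shortfall would narrow the headline gap without altering how any of them is read.

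A second reply is that recovery ratios and bounds belong in a SAP, which is not shown. That is fair for the details. But the protocol itself fixes the TPR-only analyses and the two-way reading of the ratio, and that reading is incomplete as written.

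A reader might go further and infer that discarding makes the two TPRs agree, or that an intervention effect would be shown falsely. The documents support neither. Agreement would need about 64% (HF) or 95% (CHW) of all negatives withheld. Reported TPR would stay flat against earlier years and surrounding districts, so no fall in reported TPR would be manufactured. Nor do the documents show that workers discard cassettes. The incentive remark concerns CHWs and is given as a possible factor, so extending it to facilities is inference.

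**Conclusion.** The concern holds as a foreseeable bias of the TPR contrast towards zero. Selective loss of negatives would understate discordance and pull the register-to-cassette ratio towards 1 without any change in reporting. The planned interpretation of that ratio cannot tell the two apart.

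The illustrated size ranges from about 7 points of lost gap (HF, 15% loss) to about 41 points at the CHW extreme. These figures assume that 40% and 50% are the true cassette TPRs, that reported TPR does not change, and that every missing cassette is negative. The loss rates are assumptions. The volume and positives comparisons limit the damage, so this is a change that should be made rather than a fatal flaw.

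**What to change.** In the quantitative part of Data analysis, for each point of care and month:

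1. Report the recovery ratio (cassettes counted divided by RDTs in the register, after applying the exclusion criteria) beside counted TPR. Use RDT consumption only as a secondary check, because it may include excluded tests, such as CHW tests in pregnant women or tests by nonconsenting workers.
2. Report counted TPR with bounds on the registered denominator: counted positives / registered, and (counted positives + missing cassettes) / registered.
3. Report excess positives (reported minus counted) per registered RDT. State that this is unchanged when only negatives are missing but is inflated by random loss.
4. Add cassette retention as a third explanation for movement in the register-to-cassette ratio. Read a falling gap or ratio as better reporting only alongside a high and stable recovery ratio. Where recovery is low or falling, state that the change cannot be separated from cassette loss.

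Do not make convergence conditional on both excess positives and the lower bound. Reported TPR minus the lower bound equals excess positives per registered RDT, so the two conditions are one, and under random loss that condition would reject true agreement.

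The cost is a little more analysis on totals already collected. The stated gap becomes an interval wherever recovery is incomplete.
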